4.5.4 Prohibited or Restricted Therapies

The following therapies are prohibited while the subject is on study:

- Any investigational agent or investigational medical device;
- Therapeutic doses of oral anticoagulants (e.g., warfarin or other coumarin-related agents, direct thrombin or direct FXa inhibitors, or antiplatelet agents such as clopidogrel, or chronic use of aspirin above low dose levels for cardioprotection per local applicable guidelines);
- Any other systemic anticancer treatment (e.g., chemotherapy, immunotherapy, radionuclides) and local anticancer treatment such as surgery, ablation, or embolization.

The following therapies should be avoided if possible, while the subject is on study:

- Palliative external radiation to bone metastasis for bone pain should not be performed while on study. Subjects who have such an intervention may be considered not evaluable (and may be assigned a censoring or progression date) for certain efficacy endpoints;

CONFIDENTIAL

- Erythropoietic stimulating agents (e.g., epoetin alfa and darbepoetin alfa) should not be used based on a report of increased risk of tumor recurrence and/or progression associated with erythropoietin;¹³
- Chronic co-administration of cabozantinib with strong inducers of the CYP3A4 family (e.g., phenytoin, carbamazepine, rifampin, rifabutin, rifapentine, phenobarbital, and St. John's Wort) may significantly decrease cabozantinib and erlotinib concentrations and should be avoided. Selection of alternate concomitant medications with no or minimal CYP3A4 enzyme induction potential is recommended;
- Caution must be used when discontinuing treatment with a strong CYP3A4 inducer in a subject who has been concurrently receiving a stable dose of cabozantinib or erlotinib because this could significantly increase the exposure to cabozantinib and erlotinib;
- Co-administration of cabozantinib with strong inhibitors of the CYP3A4 family (e.g., ketoconazole, itraconazole, clarithromycin, indinavir, nefazodone, nelfinavir, and ritonavir) may increase cabozantinib and erlotinib concentrations and should be avoided. Grapefruit and Seville oranges may also increase plasma concentrations of cabozantinib and erlotinib and should be avoided.

Additional information on potential drug interactions with cabozantinib and erlotinib is provided in Section 4.5.5.

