3.6 Withdrawals

Subjects may discontinue study treatment or withdraw their consent to participate in the study at any time without prejudice. The investigator may withdraw a subject from study treatment or from the study if, in his or her clinical judgment, it is in the best interest of the subject or if the subject cannot comply with the protocol.

In addition, any of the following conditions require discontinuation of the subject from study treatment:

- An adverse event or intercurrent illness that in the opinion of the investigator warrants the subject's withdrawal from study treatment;
- The investigator believes it is not in the best interest of the subject to continue on study
- Specific conditions described in the Sections 4.4 Warnings and Precautions and Guidelines for the Management of Adverse Events;
- Necessity for treatment with other anticancer treatment prohibited by protocol;
- Sexually active subjects who refuse to use medically accepted barrier methods of contraception (e.g., male condom, female condom) during the course of the study and for 4 months after discontinuation of study treatment;
- Women who become pregnant or are breastfeeding;

CONFIDENTIAL

- If the subject does not recover from his or her toxicities to tolerable Grade ≤ 2 within 6 weeks, the subject will have study treatment discontinued unless there is unequivocal evidence that the subject is benefitting. In this situation, a subject may be able to restart therapy with a dose reduction upon resolution of the toxicity and with agreement of the sponsor-investigator;
- Request by regulatory agencies for termination of treatment of an individual subject or all subjects under the protocol;
- Significant noncompliance with the protocol schedule in the opinion of the investigator;
- Progressive disease (PD) or the subject no longer experiences clinical benefit as determined by the investigator

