4.5 Concomitant Medications and Therapies

4.5.1 Anticancer Therapy

Local intervention is discouraged unless medically unavoidable. Subjects receiving local intervention (e.g., palliative radiation) are allowed to continue to receive study treatment at the investigator's discretion.

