8.4.3 Efficacy Population

The efficacy population comprises all patients who have received at least one dose of the study medication, have been evaluated for the primary endpoint, and have no significant protocol violations. This population will be used for efficacy analysis.

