8.5 Sample Size, Accrual and Study Duration

The optimal two-stage design to test the null hypothesis that $P \leq 0.025$ versus the alternative that $P \geq 0.150$ has an expected sample size of 17.32 and a probability of early termination of 0.757. If the drug is actually not effective, there is a 0.045 probability of concluding that it is (the target for this value was 0.050). If the drug is actually effective, there is a 0.198 probability of

CONFIDENTIAL

concluding that it is not (the target for this value was 0.200). After testing the drug on 11 patients in the first stage, the trial will be terminated if 0 respond. If the trial goes on to the second stage, a total of 37 patients will be studied. If the total number responding is less than or equal to 2, the combination is rejected. To allow for a few patients being not evaluable for efficacy, up to 40 subjects may be enrolled. It is estimated that two patients per month will meet eligibility criteria. As such we estimate 6 months to complete the first cohort and 15 months to complete enrollment to the second cohort. Average follow-up is expected to be 9 months to a year.

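### Section 4.5.4 leaves the efficacy handling of patients given palliative bone radiation to discretion, so a treated non-responder can be removed and replaced, or a PFS event recoded; the effect is modest and a fixed rule is cheap.

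*Combined protocol and SAP*

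**What the plan says.** **Handling in the analysis.** Section 4.5.4 lists palliative external radiation to bone metastasis for bone pain among therapies to avoid where possible, and adds: "Subjects who have such an intervention may be considered not evaluable (and may be assigned a censoring or progression date) for certain efficacy endpoints". The sentence concerns that one intervention.

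Section 8.3 does not mention radiation. It defines objective response and disease control as proportions of all subjects. It measures PFS from first treatment to RECIST 1.1 progression or death, and censors patients without progression at their last disease evaluation.

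Section 8.4.3 restricts efficacy analysis to treated patients who "have been evaluated for the primary endpoint, and have no significant protocol violations". Section 8.7 illustrates significant violations by two broad categories, eligibility and treatment plan, without a definition. Section 8.5 lets enrolment go to 40 so that some patients can be not evaluable for efficacy.

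**Permission for local treatment.** Section 4.5.1 discourages local intervention but adds: "Subjects receiving local intervention (e.g., palliative radiation) are allowed to continue to receive study treatment", at the investigator's discretion. Section 4.5.4 prohibits local anticancer treatment, with surgery, ablation and embolization as examples. Section 3.6 includes among the conditions that require stopping study treatment: "Necessity for treatment with other anticancer treatment prohibited by protocol".

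**The concern.** A censoring date and a progression date are opposite PFS outcomes for the same patient, and the 4.5.4 sentence allows either. It also allows the patient to be called not evaluable. That label feeds the requirement in 8.4.3 that the patient be evaluated for the primary endpoint. The violation clause in 8.4.3 offers a second way out, because the 4.5.4 bullet itself tells sites not to give the radiation on study.

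Section 8.2 confirms that there is no randomization or blinding, and Section 9 has weekly meetings at which observed responses are reviewed. Section 8.1 lets the analysis plan change without an amendment unless a significant feature is affected. The decision on an irradiated patient could therefore be taken with that patient's response known.

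If the need for bone radiation tends to accompany a poor course (a reasonable supposition, though the documents do not say so), selective removal raises ORR and selective censoring lengthens PFS. The primary go/no-go decision rests on three responses, so a few replaced patients can matter.

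**Working it through.** **Inputs.** From 8.5 and 8.11: null response rate 0.025, alternative 0.150; stage 1 of 11 patients, stop at 0 responses; 37 patients in total, reject the combination at 2 or fewer responses; up to 40 enrolled, so at most 40 − 37 = 3 replacements. From 8.9: median PFS is estimated under the exponential distribution. The number of irradiated patients and of PFS events is not given; I assume 1 to 3 and 28 to 37.

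**Step 1: reproduce the stated design.** Section 8.5 says the design "has an expected sample size of 17.32 and a probability of early termination of 0.757". With p = 0.025:

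- P(0 of 11) = 0.975^11 = 0.7569, the early-termination probability.
- Expected N = 11 + (1 − 0.7569) × 26 = 17.32.
- Type I error = P(1 of 11) × P(≥2 of 26) + P(2 of 11) × P(≥1 of 26) + P(≥3 of 11) = 0.21349 × 0.13708 + 0.02737 × 0.48225 + 0.00222 = 0.0447.
- The same sum at p = 0.150 gives power 0.802, so type II error 0.198.

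All four stated figures are reproduced (0.757, 17.32, 0.045, 0.198).

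**Step 2: replace known non-responders.** Suppose *a* known non-responders are dropped and replaced in stage 1 and *c* in stage 2, with a + c ≤ 3. Dropping a non-responder leaves the response count unchanged, so the rule becomes: continue with at least 1 response in 11 + a patients, succeed with at least 3 in 37 + a + c. This is the worst case, because every dropped patient is a non-responder.

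| Drops in stage 1 + stage 2 | Early termination under the null | Type I error |
|---|---|---|
| 0 + 0 | 0.757 | 0.0447 |
| 0 + 1 | 0.757 | 0.0469 |
| 1 + 0 | 0.738 | 0.0495 |
| 0 + 2 | 0.757 | 0.0491 |
| 1 + 1 | 0.738 | 0.0518 |
| 2 + 0 | 0.720 | 0.0544 |
| 0 + 3 | 0.757 | 0.0513 |
| 1 + 2 | 0.738 | 0.0542 |
| 2 + 1 | 0.720 | 0.0569 |
| 3 + 0 | 0.702 | 0.0594 |

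One replacement stays under 0.050, all three-replacement cases exceed it, and two replacements straddle it.

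**Step 3: drop without replacement.** The response count, and so the decision, does not change. The estimate moves from 3/37 = 8.1% to 3/36 = 8.3%, 3/35 = 8.6% or 3/34 = 8.8%. This and Step 2 are alternatives: a replaced patient leaves the denominator at 37.

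**Step 4: PFS.** The exponential median is ln 2 × T / d, where T is total time at risk and d the number of events. Recoding k events as censored at the same date leaves T unchanged and multiplies the median by d/(d − k).

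- k = 1: 37/36 = 1.028 to 28/27 = 1.037.
- k = 3: 37/34 = 1.088 to 28/25 = 1.120.

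The opposite option, assigning progression at radiation to a patient without RECIST progression, adds an event and removes follow-up time, and so shortens the median.

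**The case against.** The best defence is that Section 8.3 already answers the question: all subjects for response, RECIST progression or death for PFS, no radiation exception. On that view 4.5.4 contains a stray sentence that a careful analyst would ignore. This is partly right, and it is why the PFS fix can simply apply 8.3. But nothing says that 8.3 prevails, and 8.4.3 narrows all subjects to those evaluated and free of significant violations, so the sentence can still take effect.

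The size is also fairly challenged. Few patients may be affected. Dropping without replacement does not touch the decision, and a shift of under one percentage point in ORR is small beside an exact 95% interval of about 1.7% to 21.9% for 3/37. Exceeding 0.050 needs at least two of the three spare places, and with two not every split does. The replacement route comes from the 40-patient allowance and is not peculiar to radiation. PFS is secondary and only estimated. All of this stands and limits the weight of the point.

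Three stronger readings are tempting and are not supported:

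- A reader might infer that the clause covers all palliative radiation or all local therapy. It covers external radiation to bone metastasis only.
- A reader might infer that the plan provides for a choice made after the outcome is known. The text sets no timing; it only fails to prevent such a choice.
- A reader might infer that 3.6 forces irradiated patients off treatment. That condition concerns prohibited anticancer treatment, and bone radiation is on the list to avoid where possible, not on the prohibited list.

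**Conclusion.** The point holds for palliative external radiation to bone metastasis. The plan permits a selective exclusion, or either of two opposite PFS codings, without stating a rule, and Section 8 does not override it.

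The effect is modest: type I error of 0.0469 to 0.0495 with one replaced known non-responder and 0.0513 to 0.0594 with three, against 0.0447 as designed. With all three drops in stage 1, the chance of stopping early under the null falls from 0.757 to 0.702. Median PFS lengthens by about 3% to 12%. These figures rest on the assumed 1 to 3 affected patients and 28 to 37 PFS events, and on every replaced patient being a non-responder.

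There is a separate inconsistency over permission. Section 4.5.1 lets patients with local intervention continue, whereas 4.5.4 prohibits local treatment such as surgery, ablation and embolization, and 3.6 requires stopping when prohibited anticancer treatment is needed. For bone radiation the mismatch is only one of strength: 4.5.1 and the heading of the 4.5.4 list both discourage it, while the bullet under that heading is worded as a bar. I take no view on which clinical rule is right.

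**What to change.** Delete the discretionary sentence from 4.5.4 and state in Section 8 that:

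- treated patients who receive palliative bone radiation stay in the ORR and DCR denominators and are not replaced;
- their response is judged by RECIST 1.1 exactly as in 8.3. A rule making them non-responders unless response was confirmed before radiation would depart from 8.3 and is not needed;
- PFS follows the existing 8.3 rule regardless of radiation, with censoring at the radiation date as a sensitivity analysis.

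With that rule these patients no longer affect the stated error rates: type I error remains 0.0447 and power 0.802. Separately, reconcile 3.6, 4.5.1 and 4.5.4 on local treatment, including the two strengths of wording for bone radiation.

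The cost is a protocol wording change with no extra patients or procedures. The one downside is that the reported ORR may be slightly lower than if such patients were dropped.

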4.5.5 Potential Drug Interactions

Cytochrome P450 (CYP):

Please refer to the drug interaction tables at the following websites for lists of substrates, inducers, and inhibitors of selected CYP450 isozyme pathways:

[Http://medicine.iupui.edu/clinpharm/ddis/table.aspx](http://medicine.iupui.edu/clinpharm/ddis/table.aspx)

<http://www.fda.gov/Drugs/DevelopmentApprovalProcess/DevelopmentResources/DrugInteractionsLabeling/ucm080499.htm>

Cabozantinib

Data from a clinical drug interaction study (Study XL184-008) show that clinically relevant steady-state concentrations of cabozantinib appear to have no marked effect on the area under the plasma drug concentration time curve (AUC) of co-administered rosiglitazone, a CYP2C8 substrate. Therefore, cabozantinib is not anticipated to markedly inhibit CYP2C8 in the clinic,

CONFIDENTIAL

and by inference, is not anticipated to markedly inhibit other CYP450 isozymes that have lower [I]/K_i values compared with CYP2C8 (i.e., CYP2C9, CYP2C19, CYP2D6, CYP1A2, and CYP3A4). In vitro data indicate that cabozantinib is unlikely to induce cytochrome P450 enzymes, except for possible induction of CYP1A1 at high cabozantinib concentrations (30 μM).

Cabozantinib is a CYP3A4 substrate and a weak substrate for CYP2C9 (but not a CYP2D6, CYP2C8, CYP2C19, CYP2B6, or CYP1A2 substrate), based on data from in vitro studies. Results from a clinical pharmacology study, XL184-006, showed that concurrent administration of cabozantinib with the strong CYP3A4 inducer, rifampin, resulted in an approximately 77% reduction in cabozantinib exposure (AUC values) after a single dose of cabozantinib in healthy volunteers. Chronic co-administration of cabozantinib with strong inducers of the CYP3A4 family (e.g., phenytoin, carbamazepine, rifampin, rifabutin, rifapentine, phenobarbital, and St. John's Wort) may significantly decrease cabozantinib concentrations. The chronic use of strong CYP3A4 inducers should be avoided. Other drugs that induce CYP3A4 should be used with caution because these drugs have the potential to decrease exposure (AUC) to cabozantinib. Selection of alternate concomitant medications with no or minimal CYP3A4 enzyme induction potential is recommended.

Results from a clinical pharmacology study, XL184-007, showed that concurrent administration of cabozantinib with the strong CYP3A4 inhibitor, ketoconazole, resulted in a 38% increase in the cabozantinib exposure (AUC values) after a single dose of cabozantinib in healthy volunteers. Co-administration of cabozantinib with strong inhibitors of the CYP3A4 family (e.g., ketoconazole, itraconazole, clarithromycin, indinavir, nefazodone, nelfinavir, and ritonavir) may increase cabozantinib concentrations. Grapefruit and Seville oranges may also increase plasma concentrations of cabozantinib and should be avoided. Strong CYP3A4 inhibitors should be avoided and other drugs that inhibit CYP3A4 should be used with caution because these drugs have the potential to increase exposure (AUC) to cabozantinib. Selection of alternate concomitant medications with no or minimal CYP3A4 enzyme inhibition potential is recommended. In addition, cimetidine should be avoided because of its potential to interfere with CYP3A4 mediated metabolism of cabozantinib.

Erlotinib

Erlotinib is also metabolized predominately by CYP3A4. Co-treatment with the potent CYP3A4 inhibitor ketoconazole increased erlotinib AUC by 67%. When erlotinib was co-administered with ciprofloxacin, an inhibitor of both CYP3A4 and CYP1A2, the erlotinib exposure (AUC)

CONFIDENTIAL

and maximum concentration increased by 39% and 17% respectively. Dose modifications are recommended and can be made per investigator's discretion in subjects who require strong CYP3A4 inhibitors (e.g., atazanavir, clarithromycin, indinavir, itraconazole, ketoconazole, nefazodone, nelfinavir, ritonavir, saquinavir, telathromycin, treleandomycin [TAO], voriconazole, grapefruit or grapefruit juice) and CYP3A4 and CYP1A2 inhibitors (e.g., ciprofloxacin). See Table 4-2 for details. Avoid concomitant use if possible. However, subjects taking both cabozantinib and erlotinib, should follow the guidelines for cabozantinib since cabozantinib recommends avoiding CYP3A4 inhibitors.

Pre-treatment by the CYP3A4 inducer rifampicin for 7-11 days prior to erlotinib decreased erlotinib AUC by 58% to 80%. Dose modifications are recommended and can be made per investigator's discretion in subjects who require CYP3A4 inducers (e.g., rifampin, rifabutin, rifapentine, phenytoin, carbamazepine, phenobarbital, or St. John's Wort). See Table 4-2 for details. Avoid concomitant use if possible. However, subjects taking both cabozantinib and erlotinib, should follow the guidelines for cabozantinib since cabozantinib recommends avoiding CYP3A4 inducers.

Cigarette smoking: Cigarette smoking results in reduction in erlotinib AUC. Dose modifications are recommended and can be made per investigator's discretion. See Table 4-2 for details.

Drugs affecting gastric pH: Co-administration of erlotinib with omeprazole decreased erlotinib AUC by 46%, and co-administration of erlotinib with ranitidine 300 mg decreased erlotinib AUC by 33%. When erlotinib was administered with ranitidine 150 mg twice daily (at least 10 h after the previous ranitidine evening dose and 2 h before the ranitidine morning dose), erlotinib AUC decreased by 15%. Increasing the dose of erlotinib when co-administered with such agents is not likely to compensate of the loss of exposure. Dose scheduling modifications are recommended in subjects who require ranitidine and antacids (see Section 4.3).

Protein Binding: Cabozantinib is highly bound ($\geq 99.7\%$) to human plasma proteins. Therefore, highly protein bound drugs should be used with caution with cabozantinib because there is a potential displacement interaction that could increase free concentrations of cabozantinib and/or a co-administered highly protein-bound drug (and a corresponding increase in pharmacologic effect).

Other Interactions: Food may increase exposure levels of cabozantinib by 57%, fasting recommendations should be followed. Subjects should fast (with the exception of water) for at least 2 hours after eating the evening meal before taking their dose of cabozantinib. After the 2-

CONFIDENTIAL

hour fast and before going to bed, subjects are to take cabozantinib with a full glass of water (minimum of 8 oz or 240 mL) with no more food intake for one hour post-dose.

In vitro data suggest that cabozantinib is unlikely to be a substrate for P-glycoprotein, but it does appear to have the potential to inhibit the P-glycoprotein transport activity. Therefore, cabozantinib may have the potential to increase plasma concentrations of co-administered substrates of P-glycoprotein.

Cabozantinib was shown to be a substrate of drug transporter MRP2 in an in vitro assay. Administration of MRP2 inhibitors to subjects may result in increases in cabozantinib plasma concentrations.

Chronic use of modafinil should be avoided because of its potential to reduce cabozantinib exposure (see Investigator's Brochure).

Additional details regarding potential drug interactions with cabozantinib can be found in the Investigator's Brochure.

4.6 Compliance

Drug accountability will be assessed with drug dispensing and return records.

4.7 Study Drug Accountability

The investigator will maintain accurate records of receipt of all cabozantinib, including dates of receipt. In addition, accurate records will be kept regarding when and how much study treatment is dispensed and used by each subject in the study. Reasons for deviation from the expected dispensing regimen must also be recorded. At completion of the study, to satisfy regulatory requirements regarding drug accountability, all unused study drug will be reconciled and destroyed in accordance with applicable state and federal regulations.

CONFIDENTIAL

5 STUDY POPULATION

5.1 Inclusion Criteria

A subject must fully meet all of the following criteria to be eligible for the study:

1. The subject has a biopsy-proven diagnosis of adenocarcinoma of the pancreas (or recurrence of previously resected disease) with metastatic disease that is measurable per RECIST 1.1;
2. The subject must have an archived tissue sample such as a prior surgical sample or biopsy sample that is adequate for testing;
3. The subject must have EGFR and c-Met overexpressed in tumor as determined by immunohistochemistry (IHC) test score of 2+ for both markers;
4. The subject has demonstrated radiographic progression after front-line treatment (prior adjuvant therapy allowed if ≥ 6 months elapsed between end of adjuvant therapy and metastatic relapse);
5. The subject is ≥ 18 years old on the day of consent;
6. The subject has an Eastern Cooperative Oncology Group (ECOG) performance status of 0 or 1;
7. The subject has recovery to baseline or \leq Grade 1 CTCAE v.4.03 from toxicities related to any prior treatments, unless AE(s) are clinically nonsignificant and/or stable on supportive therapy;
8. The subject has organ and marrow function and laboratory values as follows within 7 days before the first dose of study treatment:
 - a. The ANC $\geq 1500/\text{mm}^3$ without colony stimulating factor support;
 - b. Platelets $\geq 100,000/\text{mm}^3$;
 - c. Hemoglobin ≥ 9 g/dL;
 - d. Bilirubin $\leq 1.5 \times$ the ULN. For subjects with known Gilbert's disease, bilirubin ≤ 3.0 mg/dL;

CONFIDENTIAL

- e. $AST/ALT \leq 3 \times$ the ULN;
 - f. Serum albumin ≥ 2.8 g/dl;
 - g. Serum creatinine $\leq 1.5 \times$ the ULN or creatinine clearance (CrCl) ≥ 40 mL/min. For creatinine clearance estimation, the Cockcroft and Gault equation should be used:
 - i. Male: $CrCl \text{ (mL/min)} = (140 - \text{age}) \times \text{wt (kg)} / (\text{serum creatinine} \times 72)$;
 - ii. Female: Multiply above result by 0.85;
 - h. UPCR ≤ 1 ;
 - i. Serum phosphorus, calcium, magnesium and potassium \geq LLN;
 - j. Prothrombin time (PT)/INR or partial thromboplastin time (PTT) test $< 1.3 \times$ the ULN *within 7 days* before the first dose of study treatment;
9. The subject is capable of understanding and complying with the protocol requirements and has signed the informed consent document;
10. The subject has a life expectancy of 12 weeks or greater;
11. The subject is able to tolerate oral medications and no evidence of ongoing malabsorption;
12. All sexually active subjects of reproductive potential must agree to use both a medically accepted barrier method (e.g., male or female condom) and a second method of birth control during the course of the study and for 4 months after the last dose of study drug(s);
13. Female subjects of childbearing potential must not be pregnant at screening. Females of childbearing potential are defined as premenopausal females capable of becoming pregnant (i.e., females who have had any evidence of menses in the past 12 months, with the exception of those who had prior hysterectomy or bilateral oophorectomy). However, women who have been amenorrheic for 12 or more months are still considered to be of childbearing potential if the amenorrhea is possibly due to prior chemotherapy, antiestrogens, low body weight, ovarian suppression or other reasons.

CONFIDENTIAL

